### **7.2 Method of Treatment Assignment**

This is an open-label study. All participants will be centrally randomized using an IRT. Before the study is initiated, each user will receive log-in information and directions on how to access the IRT.

Specific study treatments are listed in each FRACTION-Gastric Cancer Sub-Protocol. Study treatment will be dispensed at the study visits, as listed in the On-treatment Procedural Outline(s) in each FRACTION-Gastric Cancer Sub-Protocol.

All participants must be assigned a patient identification number (PID) upon providing a signed IRB/IEC-approved written informed consent. During the screening visit, the investigative site will utilize the IRT for enrollment and receive a 5-digit PID designated by BMS that will be unique across all sites. Enrolled participants, including those not dosed, will be assigned sequential PIDs starting with [REDACTED]. The PID will ultimately be composed of the site number and participant number. For example, the first participant screened (eg, enrolled) at Site Number 1 will have a PID of [REDACTED]. The following information is required for enrollment:

- Date of obtaining informed consent
- Date of birth

- Gender at birth
- Anti-PD-1, anti-PD-L1, or anti-CTLA-4 treatment experience (see [Section 5.1.3.1](#))

Once enrolled in the IRT, participants who meet all eligibility criteria will be ready to be randomized through the IRT. The following information is required for randomization:

- Participant number
- Date of birth

Randomization participant schedules will be generated and maintained by the IRT vendor. At the conclusion of the trials, BMS will receive copies of all generated participant schedules from the vendor. Because of the nature of the study design, limited early access to the randomization information will be granted to the study team to facilitate early analyses for internal decision making (early termination of study treatment arm, etc).

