Each participant who is randomized will be assigned a unique randomization number. This is not the primary identifier for the participant, but is used for the randomization schedule. The primary identifier will be the PID described above, for use on the case report form (CRF) and source documents. A participant being re-randomized in Track 2 will be assigned a different randomization number but will retain the same PID. Randomization numbers will be assigned using a Central Randomization System in the order in which participants qualify for study treatment, not in the order of study enrollment. Randomization ratios within each track will be specified in each FRACTION-Gastric Cancer Sub-Protocol. If, within a given track, study treatment arms from more than 1 FRACTION-Gastric Cancer Sub-Protocol within the FRACTION-Gastric Cancer Master Protocol are simultaneously open to enrollment, then a new participant could be assigned to any of the open study treatment arms. In Track 1, participants will be randomized to newly added study treatment arms/study treatments (through FRACTION-Gastric Cancer Sub-Protocols) in a ratio specified in each new FRACTION-Gastric Cancer Sub-Protocol. New randomization schedules for new FRACTION-Gastric Cancer Sub-Protocols will be generated. If accrual for current FRACTION-Gastric Cancer Sub-Protocols is still ongoing, participants will be allocated to the existing randomization schedule or new randomization schedule based on a pre-specified allocation ratio. Details of allocation ratio will be specified in the new FRACTION-Gastric Cancer Sub-Protocol. In Track 2, participants will be randomized to existing study treatment arm/study treatments and newly added study treatment arm/study treatments with equal probability.

Pre-specified study treatment arm caps (according to Simon 2-stage [optimal] design) will be utilized to control the accrual for each study treatment combination arm under different tracks (Tracks 1 and 2). The cap for the nivolumab in combination with ipilimumab control arm under Track 1 will be set equal to the largest cap among its corresponding experimental arms. In the event that 1 or more participants go off study without being evaluable for response (ie, with no post-baseline tumor measurements and no evidence of clinical progression or death due to disease progression), the enrollment cap for that study treatment arm may be correspondingly raised if

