**Track 1 - Anti-PD-1, Anti-PD-L1, and Anti-CTLA-4 Treatment-naïve Participants**

The following additional analyses will be performed for Track 1 anti-PD-1, anti-PD-L1, and anti-CTLA-4 treatment-naïve participants combined at end of Stage 2. These efficacy analyses will be performed when the study treatment arms have been fully enrolled and followed up for at least 6 months. A descriptive odds ratio and estimate of the difference in ORRs, along with corresponding 2-sided 95% CIs, will be provided to evaluate differences between the 2 randomized study treatment arms (FRACTION-Gastric Cancer study treatment combination arm and nivolumab in combination with ipilimumab control arm). Additionally, for each study treatment arm, the ORR and corresponding 95% CIs will be calculated using Clopper-Pearson method. A descriptive hazard ratio and corresponding 2-sided 95% CI of PFS and OS will be estimated in a Cox proportional hazards model using study treatment as a single covariate to evaluate difference between the 2 study treatment arms (experimental and control arms). The PFS and OS curves for each study treatment arm will be estimated. Two-sided 95% CIs for median PFS and OS will be computed. PFSR at 24 weeks and survival rates at certain time points (eg, 2 years) will be estimated. Associated 2-sided 95% CIs will be calculated.

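### Does the Track 1 comparison with nivolumab plus ipilimumab need allocation-period strata and a written concurrent-control rule?

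*Combined protocol and SAP*

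**What the plan says.** Section 10.3.1 adds a set of Track 1 analyses at the end of Stage 2, once the arms are fully enrolled and have at least 6 months of follow-up. For response, "A descriptive odds ratio and estimate of the difference in ORRs, along with corresponding 2-sided 95% CIs, will be provided", the purpose being "to evaluate differences between the 2 randomized study treatment arms": one combination arm and the nivolumab plus ipilimumab control. Hazard ratios for PFS and OS are to be "estimated in a Cox proportional hazards model using study treatment as a single covariate to evaluate difference between the 2 study treatment arms". No stratum is named, and nothing says whether controls randomised before a combination opened are used.

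Section 7.2 describes the allocation. Track 1 participants are randomised to newly added arms "in a ratio specified in each new FRACTION-Gastric Cancer Sub-Protocol". If arms from more than one Sub-Protocol are open, "then a new participant could be assigned to any of the open study treatment arms". While accrual to older Sub-Protocols continues, "participants will be allocated to the existing randomization schedule or new randomization schedule based on a pre-specified allocation ratio". The same section caps the Track 1 control arm at the largest cap among its corresponding experimental arms.

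Section 10.1 sends statistical considerations specific to new combinations to the Sub-Protocols. Section 10.3 describes itself as a summary, with an SAP to be finalised before database lock. The detailed SAP text and the Sub-Protocols are not part of the document reviewed.

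**The concern.** Arms in a platform trial open and close, and one control arm can serve several combinations. If the combination-to-control ratio differs between periods and later participants have a different prognosis, an unstratified contrast mixes the treatment effect with the calendar effect. The extreme case is a control group partly recruited before the combination opened: those controls were never randomised against it.

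The primary objective is framed relative to nivolumab plus ipilimumab when applicable, and Section 10.1 lists the relative performance of arms among the things the sponsor reviews before a final determination. A pooled estimate presented as a randomised comparison could therefore mislead, and the usual remedy would be to stratify by allocation period or to restrict to concurrent controls.

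**Working it through.** **What can be reproduced.** The comparison with control has no stated sample size, power or allocation ratio. The only related figures are those of the Track 1 Simon design (4/19, 15/54). Exact binomial calculation gives 0.673 for stopping at Stage 1 and 0.0482 for the false positive rate at 20% ORR, and 0.9045 for power at 40%. The protocol states 67%, 5% and 90%, so 54 is a sound arm size for what follows.

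**Bias of the pooled ORR difference.** With no true effect and a drift of *D* points between two periods:

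bias = *D* × (share of combination arm in period 2 − share of control arm in period 2).

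The starting ORR is 24% (Section 3.2.1, nivolumab plus ipilimumab in Study CA209032). The splits and drifts are assumptions. For *D* = 10:

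- Ratio change, combination:control 20:20 then 34:11: 10 × (34/54 − 11/31) = 10 × (0.630 − 0.355) = 2.7 points.
- Control filled in parallel to its cap, 20:20 then 34:34: 10 × (34/54 − 34/54) = 0.
- One third of 54 controls non-concurrent: 10 × (1 − 36/54) = 3.3 points.
- Two thirds non-concurrent: 10 × (1 − 18/54) = 6.7 points.

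A 5-point drift halves each figure. With no drift, all are zero.

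**Error and coverage.** Root mean squared error (RMSE) = √(bias² + SD²). For the ratio change with ORR rising to 34%, √(2.75² + 10.12²) = 10.5 points. Exact enumeration gives the following, where the alternative is the period-stratified Mantel-Haenszel difference for the ratio change and the concurrent-only difference otherwise:

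| Scenario | Period 2 ORR | Pooled bias | Pooled coverage | RMSE pooled | RMSE alternative |
|---|---|---|---|---|---|
| Ratio change | 14% | −2.75 | 93.9% | 9.27 | 9.18 |
| | 19% | −1.37 | 94.2% | 9.38 | 9.62 |
| | 29% | +1.37 | 93.6% | 10.00 | 10.27 |
| | 34% | +2.75 | 92.7% | 10.48 | 10.49 |
| One third non-concurrent | 14% | −3.33 | 91.7% | 7.72 | 7.47 |
| | 19% | −1.67 | 94.1% | 7.84 | 8.44 |
| | 29% | +1.67 | 94.2% | 8.81 | 9.76 |
| | 34% | +3.33 | 93.0% | 9.57 | 10.19 |
| Two thirds non-concurrent | 14% | −6.67 | 84.2% | 9.83 | 9.44 |
| | 19% | −3.33 | 92.5% | 8.46 | 10.68 |
| | 29% | +3.33 | 92.9% | 9.19 | 12.35 |
| | 34% | +6.67 | 87.9% | 11.06 | 12.89 |

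The alternative has the lower RMSE only for the 10-point fall. It ties at +10 points under the ratio change and loses elsewhere.

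**Price in precision.** With 24% ORR in both arms and no drift, the 95% half-width is 1.96 × √(0.24 × 0.76 × (1/54 + 1/n)), where n is the number of controls used. It is 16.1 points for n = 54, 18.0 for n = 36 and 22.8 for n = 18. Dropping non-concurrent controls therefore widens the interval by about 12% or 41% in the one-third and two-thirds cases. Under the ratio change, stratifying costs about 3% to 5%.

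**PFS.** Simulation used exponential times from the 12-month rate of 17% in Section 3.2.1 and an assumed period 2 hazard multiplied by 1.25 or 0.8. The pooled null hazard ratio is 1.06 or 0.94 under the ratio change (coverage about 94%), and 1.08 or 0.93 with one third non-concurrent (93.5% to 93.7%).

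**The case for a change.** The strongest reply is that this design invites the problem. Arms are meant to open and close quickly, the Track 1 ratio is left to each Sub-Protocol, and the eligible population changed when Revised Protocol 03 (05-Feb-2019) added esophageal cancer, which makes drift plausible. If most controls preceded the combination, the harm is not small: with two thirds non-concurrent and a 10-point drift, pooled ORR coverage falls to 84.2% or 87.9%. In a separate simulation assuming a 3-month median PFS and a period 2 hazard 0.7 times that of period 1, the pooled hazard ratio was 0.79 with 80% coverage. The remedy needs no new data, since "At the conclusion of the trials, BMS will receive copies of all generated participant schedules from the vendor". A descriptive estimate still needs a defined comparison set.

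The last point stands, and so does the arithmetic. But the damaging cases require counting as controls people who were never randomised against the combination, whereas Section 10.3.1 speaks of two randomised arms and Section 7.2 ties the control arm to its corresponding experimental arms. The natural reading is a concurrent comparison. Under that reading only the ratio-change case remains, and the example used for it leaves the control arm at 31, which is 23 short of a cap of 54. A cap is only a ceiling, so this can happen, but nothing in the document shows that it did.

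**Conclusion.** No change to the plan is called for. The Master Protocol leaves the control set and any period stratum unstated. That is detail which it assigns to the Sub-Protocols, where the ratios are set, and to the SAP. An analyst who found that the ratio had shifted, or that early controls were in the data, would ordinarily report their numbers and show a concurrent or period-stratified estimate beside the planned one.

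Making the stratified analysis the main one is a bias-variance choice with no clear gain. Under a ratio change, the bias it removes is at most 2.7 ORR points for drifts up to 10 points, inside an interval of roughly ±17 to ±20 points. With a constant ratio, no drift or a single allocation period, the planned analysis is already unbiased.

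The stakes are limited as well. The estimates are labelled descriptive, the Simon boundaries use each arm's own responses, and Section 10.3.4 plans no formal inference needing an adjusted significance level. Amendment 06 records early closure, so a comparison conditional on full enrolment may never be run.

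These sizes rest on assumed splits and drifts. The conclusion would weaken if the Sub-Protocols showed a large share of non-concurrent controls pooled without comment.

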**10.3.2 Safety Analyses**

All safety analyses will be performed on the treated population.

Endpoint	Statistical Analysis Methods
Incidence of AEs, SAEs, and AEs leading to discontinuation and deaths AEs will be graded according to CTCAE Version 4.03.	Frequency distribution of treated participants with AE using the worst CTC grade on treatment. Participants will be counted once at the PT level, once at the SOC level, and once in the “Total subject” row at their worst CTC grade, regardless of SOC or PT.
Laboratory abnormalities Laboratory values will be graded according to CTCAE Version 4.03.	Laboratory shift table using worst CTC grade on treatment per participant.

Abbreviations: CTC = Common Terminology Criteria; PT = preferred term; SOC = system organ class.

Same treatments under different tracks with different populations may be combined for safety analyses.

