### DOCUMENT HISTORY

Document	Date of Issue	Summary of Change
Protocol Amendment 06	13-Aug-2021	Due to early closure of the trial for reasons unrelated to safety, the study schedule was adjusted to remove retreatment/re-randomization options, Response Follow-up, and Survival Follow-up periods for all parts of the study. No changes were made to the Treatment period or Safety Follow-up period.
Administrative Letter 04	30-Sep-2020	Updates to staff/contact information for the Medical Monitor
Administrative Letter 03	12-Dec-2019	Updates to staff/contact information for the Medical Monitor
Revised Protocol 05	13-Sep-2019	The nivolumab management algorithms (Appendix 6) were updated to include the myocarditis adverse event management algorithm. Esophagus Cancer Subscale (ECS) from the Functional Assessment of Cancer Therapy-Esophageal (FACT-E) patient-reported outcome assessment was added. Medical Monitor/Study Direction information was updated.
Revised Protocol 04	03-May-2019	Collection timing and assessment of pretreatment tumor biopsy was clarified. Additional approval information for pembrolizumab was added. Option to utilize a local pathologist for tumor biopsy assessments was removed. Language was updated to indicate that vaccines containing live/attenuated viruses are prohibited. Processing of tumor biopsies was updated. Language describing participants who are imprisoned and Appendix 02 (Study Governance Considerations) were updated to align with the current BMS Protocol Model Document.
Administrative Letter 02	05-Mar-2019	Screening biopsy requirement was corrected.
Revised Protocol 03	05-Feb-2019	The FRACTION-Gastric Master Protocol was revised to expand indication to esophageal cancer based on the results of CheckMate-032 clinical study. Added clarification on timing and eligibility for efficacy assessment scans at FU1 and FU3.
Administrative Letter 01	24-Jul-2018	Change in Medical Monitor Information
Revised Protocol 02	14-Dec-2017	Revised to allow participants to continue on study treatment for up to 2 years, and re-treatment is not permitted. Stratification by PD-L1 is no longer a factor. Typographical errors were corrected.
Revised Protocol 01	15-Sep-2016	Incorporates Amendment 01
Amendment 01	15-Sep-2016	Typographical errors were corrected, and clarifications were made for consistency.
Original Protocol	12-Aug-2016	Not applicable

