## 5 STUDY DESIGN

### 5.1 Overall Design

This is a rolling, Phase 2, adaptive study that will evaluate the preliminary efficacy, safety, tolerability, PK, and pharmacodynamics of novel FRACTION-Gastric Cancer study treatment combinations in participants with advanced GC and/or EC. The details pertaining to the specific study treatment regimens are provided in each FRACTION-Gastric Cancer Sub-Protocol.

Participants will be enrolled in 1 of the 2 tracks. Participants who are anti-PD-1, anti-PD-L1, and anti-CTLA-4 treatment naïve will be enrolled for Track 1. Participants who have had prior anti-PD-1, anti-PD-L1, or anti-CTLA-4 treatment will be assigned to Track 2, as outlined in [Figure 5.1-1](#) and described in [Section 5.1.1](#).

Participants on Tracks 1 and 2 will begin on the Treatment Phase (with a total duration of approximately 2 years). Tumor assessments will be conducted according to the timing described in each FRACTION-Gastric Cancer Sub-Protocol.

[figure not shown]
Participants in Tracks 1 and 2 will be treated until completion of the Treatment Phase, progression, toxicity, or protocol-specified discontinuation (see [Section 8.1](#)). The decision to continue treatment beyond investigator-assessed progression is possible (for up to completion of that Treatment Phase) and should be discussed with the BMS Medical Monitor (or designee) and documented in the study records (see [Section 7.4.2](#)). In addition, a participant with PD has the option to enter into Track 2, assuming that he/she continues to fulfill all eligibility criteria at each new randomization point, including a life expectancy of  $\geq 3$  months (see [Section 5.1.1](#)).

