### **8.1.2 Study Treatment Combination Arm Discontinuation Criteria**

In the event that 20% or more of study participants in a novel FRACTION-Gastric Cancer study treatment combination arm of a given track, at any given time, meet any of the toxicity criteria for permanent discontinuation (as described in [Section 8.1.1](#)), then consideration will be given to discontinue that FRACTION-Gastric Cancer study treatment combination arm in that track. This will include early side effects seen with combination agents and longer-term effects such as endocrinopathies. This action will be taken in consultation with the SMB and will consider other pertinent facts in coming to a decision, including the toxicity profile of that combination seen outside FRACTION-Gastric Cancer, participant benefit as measured by anti-tumor response, and comparison to nivolumab in combination with ipilimumab.

Discontinuation of a study treatment combination arm in a given track for any reason will not lead to discontinuation for that combination in all tracks. Safety of all open-label study treatment combination arms in other tracks that contain the same agent (or agents) will be assessed by SMB and the Sponsor. In the event of serious, unexpected, or life-threatening emergent toxicities, relevant study treatment combination arms may then be modified to maintain the safety of participants. Decisions on such steps and the re-initiation of any study treatment combination arms that had been stopped would be made by SMB in consultation with the Sponsor and relevant authorities (eg, IRB/IEC).

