### 10.3 Statistical Analyses

The statistical analysis plan will be developed and finalized before database lock. Below is a summary of planned statistical analyses of the primary and secondary endpoints.

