**Overall Rationale for the Revised Protocol 02, 14-Dec-2017**

The FRACTION-Gastric Master Protocol was revised to allow participants with complete response, partial response, or stable disease to continue treatment for up to a total duration of 2 years. Additionally, PD-L1 status was removed as a stratification factor.

Summary of key changes of Revised Protocol 02		
Section Number & Title	Description of Change	Brief Rationale
Section 2, Schedule of Activities; Table 2-2, Baseline for Re-randomization Procedural Outline; Section 3.1.1.2, Specific Attributes of the FRACTION Program Design; Section 5.1, Overall Design; Section 5.1.1, FRACTION-Gastric Cancer Tracks 1 and 2 Design; Figure 5.1.1-1, Tracks 1 and 2 Study Design Schematic; Section 5.1.3.2, Treatment; Section 5.1.3.3, Follow-up; Section 5.4.1, Rationale for Duration of Therapy	Participants will receive treatment of up to 2 years total duration.	Emerging data suggest that patients may derive clinical benefit beyond 6 months of immunotherapy. Therefore, patients will continue on study treatment for up to 2 years and re-treatment is not permitted.
Table 2-1, Screening Procedural Outline; Section 5.1.3.1, Screening; Section 6.1, Inclusion Criteria “2.e.i.5” and “2.e.ii.1”; [REDACTED]	Changes made to reflect that PD-L1 status will no longer be a stratification factor, and therefore, results will no longer be needed before randomization	Expression of PD-L1 on tumor is not required for clinical benefit based on a randomized clinical trial in gastric cancer (ATTRACTION 2). Therefore, PD-L1 will not be used as a stratification factor.
Table 2-1, Screening Procedural Outline	
 
1. Duration of randomization prior to first dose extended
 
2. Data to be collected on toxicities from treatment with prior immunotherapies
 
	
 
1. To allow patients to complete all the post-randomization procedures required for a sub-protocol, duration between randomization and start of treatment can be extended to allow for completion of study-related tests.
 
2. For patients previously treated with PD-1/PD-L1/CTLA-4, enrolling directly into Track 2, we will collect additional data on details of adverse events with prior immunotherapies.
 

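### Section 10.3.2 summarises adverse events only as crude proportions of treated participants, so differences in realised time on drug mix with toxicity when arms are compared or tracks pooled

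*Combined protocol and SAP*

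**What the plan says.** Section 10.3.2 defines the adverse-event analysis as "Frequency distribution of treated participants with AE using the worst CTC grade on treatment". Each participant is counted once per preferred term, once per system organ class and once overall. The analysis set is fixed: "All safety analyses will be performed on the treated population". Pooling is optional: "Same treatments under different tracks with different populations may be combined for safety analyses". The section lists no summary of exposure, no rate per person-time and no time-to-event method. It does not say how its on-treatment period relates to the window in Table 2-3 and Section 9.2.1, which runs to 100 days after the last dose.

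On duration, Section 5.1 sets one limit for both tracks: "Participants on Tracks 1 and 2 will begin on the Treatment Phase (with a total duration of approximately 2 years". Section 5.1.3.2 ends treatment earlier for progression, clinical deterioration, toxicity or other discontinuation criteria. The Document History dates the longer limit to Revised Protocol 02 of 14-Dec-2017: "Revised to allow participants to continue on study treatment for up to 2 years, and re-treatment is not permitted".

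On use, safety is the secondary objective in Table 4-1. When an arm is considered for closure on toxicity grounds, Section 8.1.2 weighs, among other things, "participant benefit as measured by anti-tumor response, and comparison to nivolumab in combination with ipilimumab".

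**The concern.** A proportion of participants with an event has no time base. If one arm controls disease for longer, its participants stay on drug longer and have more opportunity for a first event, even when the event rate per month equals that of the control. The more effective arm then looks more toxic, and an arm whose participants progress early looks safer. A pooled figure for one treatment across tracks also depends on the mix of treatment-naïve and treatment-experienced participants, who may stay on drug for different lengths of time.

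The protocol accepts the premise. Section 5.4.1 says that longer treatment brings further toxicity risk, and Section 8.1.2 asks that late effects such as endocrinopathies be counted. At stake is how the secondary safety results are read against the control, and the safety information that Sections 10.1.1 and 10.1.2 bring into decisions on continuing an arm.

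**Working it through.** **The plan's own figure.** Section 10.1 states an 88% chance of seeing an adverse event with a true rate of 5% among 41 participants. 1 − 0.95^41 = 0.878, so it reproduces. The 5% is a per-participant figure with no stated follow-up time.

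**Inputs from the protocol.**
- 12-month progression-free survival rates of 17% (nivolumab plus ipilimumab) and 8% (nivolumab alone) in an earlier study, Section 3.2.1. They serve only as two plausible speeds of leaving treatment.
- Cap C = 104 weeks = 104 × 7 / 30.4375 = 23.9 months, Section 5.1.
- Collection window w = 100 days = 3.29 months, Table 2-3.

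**Assumptions, not protocol figures.** Time on drug is exponential with rate m = −ln(PFSR)/12. The first event has a constant rate r = 0.05 per month, the same in both arms.

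**Exposure.** m = 0.2105 (8%) and 0.1477 (17%). Mean time on drug is (1 − exp(−mC))/m = 4.7 and 6.6 months.

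**Crude incidence on treatment.** P = r/(r+m) × (1 − exp(−(r+m)C)).
- 8%: 0.05/0.2605 × (1 − 0.0020) = 19.2%
- 17%: 0.05/0.1977 × (1 − 0.0089) = 25.1%

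**With the 100-day window.** P* = 1 − exp(−rw) × (1 − P), where exp(−0.05 × 3.29) = 0.8485.
- 8%: 1 − 0.8485 × 0.8084 = 31.4%
- 17%: 1 − 0.8485 × 0.7493 = 36.4%

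The gap is 5.9 points on treatment and 5.0 points with the window.

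**Rate per person-time.** Expected person-months to first event or end of treatment are P/r = 3.83 and 5.01. Then 0.192/3.83 and 0.251/5.01 both give 5.0 per 100 person-months. The equality follows from the constant-rate assumption. It shows what the rate recovers and the proportion does not.

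**Sensitivity (on treatment, same cap).** If the rate falls to a fraction f of r after 24 weeks (c = 5.52 months), incidence is P(c) + exp(−(r+m)c) × fr/(fr+m) × (1 − exp(−(fr+m)(C−c))).

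| Assumption | PFSR 8% | PFSR 17% |
|---|---|---|
| r = 2% per month, constant | 8.6% | 11.7% |
| r = 5% per month, constant | 19.2% | 25.1% |
| r = 10% per month, constant | 32.2% | 40.3% |
| r = 5%, halved after 24 weeks | 17.1% | 21.5% |
| r = 5%, no first events after 24 weeks | 14.6% | 16.8% |

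**Scale.** With 54 participants in an arm (the Track 1 maximum), one standard error of a 25.1% proportion is √(0.251 × 0.749/54) = 5.9 points. The shift is about that size, but it is systematic.

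**Change of duration rule.** At 17% and r = 5%, a 24-week cap against a 104-week cap gives 16.8% versus 25.1% on treatment, or 29.4% versus 36.4% with the window. This shows the direction only. The earlier limit is inferred from the Revised Protocol 02 rationale in Appendix 9, which speaks of benefit beyond 6 months, and the number of participants treated under it is not given.

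**The case against.** Several points on the other side stand.

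- A reader might infer that the protocol permits different durations by arm or track. It does not. Both tracks have the same limit of about 2 years, and the master protocol states no arm-specific maximum. Only realised exposure can differ.
- A reader might infer that crude incidence follows exposure instead of toxicity. The table above refutes this. At 17%, moving the event rate from 2% to 10% per month moves incidence from 11.7% to 40.3%, far more than exposure does. The proportion reflects both.
- A reader might infer that no time-based analysis exists anywhere. Section 10.3 calls itself a summary and adds: "The statistical analysis plan will be developed and finalized before database lock". That plan and the sub-protocols are not in the file and may contain exposure tables. Against this, Sections 10.3.1, 10.3.3.3 and 10.3.4 each send detail to the statistical analysis plan, and Section 10.3.2 does not.
- The effect of the protocol version cannot be sized. Re-treatment ended at the same revision, so a single 24-week cap may understate earlier exposure. Arms randomised concurrently in Track 1 share one duration rule.
- Arm closure under Section 8.1.2 does not rest on the Section 10.3.2 table. It concerns participants meeting toxicity criteria for permanent discontinuation, is taken with the Safety Monitoring Board, and weighs benefit.
- The endpoint is incidence, and a participant-level proportion answers it. That is a reason to keep the crude table. It does not make the proportion a fair basis for comparing arms with unequal exposure.
- Cutting everyone at 24 weeks is not a sufficient remedy. Incidence still differs at equal rates (14.6% versus 16.8%), and late effects are lost.

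**Conclusion.** The point holds as a low-cost improvement to the safety analysis. As written, Section 10.3.2 commits to crude proportions only, and realised time on drug depends on how well an arm controls disease. Comparisons with nivolumab plus ipilimumab, and pooled-track figures, therefore combine toxicity with exposure.

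Under the stated assumptions the distortion is about 6 points on treatment and 5 points with the 100-day window. It falls to about 2 points on treatment if no first event occurs after 24 weeks. These sizes rest on exponential time on drug, an assumed event rate common to both arms, and disease-control figures from another study. They are not predictions for any arm here. The documents do not show that an arm was or would be wrongly stopped, and they do not allow the duration change to be quantified.

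**What to change.** Keep the crude table in Section 10.3.2 and add the following, by arm within track:

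1. A summary of time on treatment.
2. Exposure-adjusted incidence rates for adverse events, serious adverse events and adverse events leading to discontinuation. Person-time runs from first dose to first event or to the end of the collection window (last dose plus 100 days, or earlier if collection ends earlier). Count events over the same window. Split at 24 weeks so that early and later rates are both visible.
3. A statement that these rates are read beside the crude figures in any comparison with nivolumab plus ipilimumab, and are stratified by track when tracks are combined.
4. A separate display of participants treated under the duration rule before Revised Protocol 02, only if there were any.

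If the statistical analysis plan already contains these, a cross-reference from Section 10.3.2 is enough. No change is proposed to the 20% trigger in Section 8.1.2.

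The cost is one extra set of tables from dose dates and event onset dates already collected, with no change to conduct. The limitation is that each rate assumes a roughly constant hazard within its interval, and person-time after the last dose counts as time at risk.
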